CNS	Central nervous system
CR	Complete response
CRF	Case report form
CT	Computed tomography
CTCAE	Common Toxicity Criteria for Adverse Events
CV	Coefficient of variation
CYP	Cytochrome P450
D/C	Discontinue

Version Date: 11APR2023

Abbreviation or Term ¹	Definition/Explanation
ECOG	Eastern Cooperative Oncology Group
eCRF	Electronic case report form
DLT	Dose Limiting Toxicity
ECG	Electrocardiogram
Eg	Exempli Gratia (for example)
FACS	Fluorescence-Activated Cell Sorting
FDA	Food and Drug Administration
FDG-PET	Fluorodeoxyglucose (FDG)-positron emission tomography (PET)
GCP	Good Clinical Practice
GFR	Glomerular filtration rate
GGT	Gamma-glutamyltransferase
GLP	Good laboratory practice
HBsAg	Hepatitis B surface antigen
HBV	Hepatitis B virus
HCO ₃ -	Bicarbonate
HCV	Hepatitis C virus
HIV	Human immunodeficiency virus
HR	Heart rate
hr	Hour or hours
IC ₅₀	Half maximal inhibitory concentration
i.e.	Id est (that is)
IEC	Independent ethics committee
IND	Investigational New Drug
INR	International normalized ratio
IRB	Institutional review board
IU	International unit
IV	Intravenous, intravenously
LDH	Lactate dehydrogenase
LLQ	The lower limit of quantitation
MedDRA	Medical Dictionary for Drug Regulatory Activities
MID	minimal important difference

Abbreviation or Term ¹	Definition/Explanation
MRI	Magnetic resonance imaging
MRSD	The maximum recommended starting dose
MTD	Maximum tolerated dose
NOAEL	No-observed-adverse-effect level
NOEL	No-observed-effect-level
PCORI	the Patient-Centered Outcomes Research Institute
PD	Pharmacodynamic(s)
PFS	Progression-Free Survival
PK	Pharmacokinetic(s)
PRO	Patient Reported Outcome
PO	Per os (administered by mouth)
PR	Partial response
PT	Prothrombin time
PTT	Partial thromboplastin time
QC	Quality control
RBC	Red blood cell
QD	Once-daily
QOL	Quality of Life
QTc	QT interval corrected
QTcF	QT interval corrected using Fredericia equation
SAE	Serious adverse event
SD	Standard deviation or stable disease
$T_{1/2}$	Terminal elimination half-life
T_3	Triiodothyronine
T_4	Thyroxine
T_{max}	Time of maximum observed concentration
TID	Three times daily
TSH	Thyroid-stimulating hormone
ULN	The upper limit of normal
ULQ	The upper limit of quantitation
UV	Ultraviolet

Version Date: 11APR2023

Abbreviation or Term ¹	Definition/Explanation
WBC	White blood cell
WOCBP	Women of childbearing potential
WONCBP	Women of nonchildbearing potential

¹ All of these abbreviations may or may not be used in the protocol.

Version Date: 11APR2023

PROTOCOL SIGNATURE

I confirm that I have read this protocol, and I will conduct the study as outlined herein and according to the ethical principles stated in the latest version of the Declaration of Helsinki, the applicable ICH guidelines for good clinical practice, and the applicable laws and regulations of the federal government. I will promptly submit the protocol to the IRB for review and approval. Once the protocol has been approved by the IRB, I understand that any modifications made during the course of the study must first be approved by the IRB prior to implementation except when such modification is made to remove an immediate hazard to the subject.

I will provide copies of the protocol and all pertinent information to all individuals responsible to me who assist in the conduct of this study. I will discuss this material with them to ensure that they are fully informed regarding the study treatment, the conduct of the study, and the obligations of confidentiality.

Note: This document is signed electronically through submission and approval by the Principal Investigator in the University of Utah IRB Electronic Research Integrity and Compliance Administration (ERICA) system.

Version Date: 11APR2023

STUDY SUMMARY

Title	A Phase II Randomized Controlled Trial of a Supplement Containing Quercetin, Bromelain, Rye Flower Pollen, and Papain on Reducing the Severity of Radiation-Induced Prostatitis
Short Title	Q-Urol
Protocol Identifiers (IRB – internal)	129154
Phase	Phase II
Design	An asymmetric two-sided group sequential design will be used with an interim analysis for efficacy and futility.
Study Duration	Up to three years.
Study Center(s)	Huntsman Cancer Institute
Objectives	Primary Objective: To assess the difference in prostatitis symptoms in men with localized prostate cancer following brachytherapy taking Q-Urol relative to placebo.
	 Secondary Objectives: To assess Health-Related Quality of Life (HRQOL) in the urologic, rectal, sexual, hormonal, mental and overall physical domains of men receiving either placebo or supplement after definitive brachytherapy. To assess if the Q-Urol has any significant impact on serum biomarkers of inflammation relative to placebo. To access if the addition of Q-Urol introduces any
	additional toxicity relative to placebo.
Number of Subjects	Up to 140, 70 per arm.
Diagnosis and Main Eligibility Criteria	Key Inclusion Criteria:Male subjects aged ≥ 18 years.
	Histologically proven prostate adenocarcinoma who have selected treatment with brachytherapy with or without external beam radiation, with or without androgen deprivation therapy.
	Fluent in speaking and reading English.
	• ECOG Performance Status ≤ 1
	Key Exclusion Criteria:
	• Baseline AUA symptom scores > 15.
	ſ

Version Date: 11APR2023

	Prior diagnosis of chronic prostatitis type II-IV.	
	• The subject has received systemic therapy intended for the treatment of prostatitis (including herbal supplements) ≤ 14 days of starting study treatment.	
	• The subject has received a fluoroquinolone antibiotic (e.g. ciprofloxacin, norfloxacin, ofloxacin levofloxacin, etc.) ≤ 3 days of starting study treatment.	
	The subject is actively on anti-inflammatory medications for other medical conditions, unless approved by PI.	
	• The subject has undergone transurethral resection of the prostate (TURP).	
Study Product, Dose, Route, Regimen	Q-Urol (proprietary blend 375 mg plus 37.5 mg calcium) two capsules taken twice daily.	
Duration of administration	Six weeks after brachytherapy placement.	
Reference therapy	Standard of care supportive therapy after brachytherapy placement.	
Statistical Methodology	There are two planned analyses of the primary endpoint variable, an interim analysis at $N1 = 21$ patients per groups and a final analysis at $N = 70$ patients per group. Two sample t -tests will be used for both the analysis. A single interim analysis is planned after $N1 = 21$ subjects per group have outcome data. The interim and final analysis will compare the treatment and control means using nominal t statistics (control minus treatment). If the t statistic has a value less than -1.16 at the interim analysis the trial will be terminated for futility. If the t statistic has a value greater than 2.85 at the interim analysis the trial will be terminated for efficacy.	
	If the study is not terminated for efficacy or futility at the interim analysis an additional $N2 = 49$ patients per group will be accrued for a total of $N = 70$ patients per group. If the interim analysis is done at the planned sample size (21 patients per group) the treatment will be deemed efficacious at the final analysis if the t statistic has a nominal value greater than 1.67.	
	In addition to formal testing for a difference between groups, the mean change between groups and the mean change within each group together will be reported together with 95% confidence intervals.	

Version Date: 11APR2023

SCHEMA

[figure not shown]

Figure 1 : Study Schema

Version Date: 11APR2023

1 OBJECTIVES

1.1 Primary Objective

1.1.1 To assess the difference in prostatitis symptoms in men with localized prostate cancer following brachytherapy taking Q-Urol relative to placebo.

Primary Endpoint: The mean peak score of the National Institutes of Health-Chronic Prostatitis Symptom Index (NIH-CPSI) measured at six weeks post brachytherapy.

1.2 Secondary Objective(s)

1.2.1 To assess Health-Related Quality of Life (HRQOL) in the urologic, rectal, sexual, hormonal, mental and overall physical domains of men receiving either placebo or supplement after definitive brachytherapy.

Secondary Endpoint: Patient questionnaires administered pre- and post-study therapy: The Expanded Prostate Cancer Index Composite (EPIC), The International Prostate Symptom Score (I-PSS), The Rectal Function Assessment Score (R-FAS), and the Sexual Health Inventory for Men (SHIM).

1.2.2 To assess if the Q-Urol has any significant impact on serum biomarkers of inflammation relative to placebo.

Secondary Endpoint: Inflammation markers pre and post brachytherapy: erythrocyte sedimentation rate, C-reactive protein, and prostate-specific antigen (PSA)

1.2.3 To access if the addition of Q-Urol introduces any additional toxicity relative to placebo.

Secondary Endpoint: Frequency of adverse events (AEs) will be collected and characterized by type, severity (as defined by CTCAE, version 5.0), seriousness, duration, and relationship to study treatment.

1.2.4 To assess the effect on prostatitis-related pain in men with localized prostate cancer following brachytherapy taking Q-Urol relative to placebo.

Secondary Endpoint: The number of days during the 28 days post-brachytherapy that any medication is taken for the treatment of prostate-related pain.

2 BACKGROUND

2.1 Prostate Cancer and Brachytherapy Induced Prostatitis

Prostate cancer is the most commonly diagnosed cancer in men with an estimated 174,650 new cases and 31,620 deaths projected in 2019. At diagnosis, approximately 85% of men

Version Date: 11APR2023

will have disease localized to the prostate, and most will elect to have either surgical therapy or radiation treatment with curative intent.

Brachytherapy (seed implant), either alone or combined with external beam radiation therapy, is an established care standard for localized prostate cancer. The physical trauma of the procedure and the continuing exposure of the prostate tissue, neurovascular bundles, bladder neck, and anterior rectal wall over the ensuing 3-6 months to radiation and its effects results in an inflammatory state with symptoms identical to chronic prostatitis type IIIA or IIIB. Virtually 100% of subjects will experience these uncomfortable symptoms, with severity typically peaking around weeks 4-6 post-implant, before gradually improving over the ensuing 6-12 months. Like chronic prostatitis, the mainstay of comfort therapy for these subjects is the use of alpha-blockers, NSAIDs, steroids, anticholinergics, antidiarrheals, and phosphodiesterase inhibitors.

Prostatitis symptoms can result in significant distress, pain, nocturia related-fatigue, loss of work and productivity. Improving the side-effect profile of brachytherapy without adding a significant risk of other toxicities or a decrease in oncologic efficacy is highly desirable.

2.2 Rationale for Q-Urol

Q-Urol is a commercially available supplement whose key active ingredient is Quercetin.

Quercetin has been shown to have the following biological properties:

- A potent free radical scavenger² and antioxidant.³
- An anti-inflammatory agent, which reduces inflammation by inhibiting interleukin-6, interleukin 8, tumor necrosis factor, and NF-κB. 4-7
- In animal models of inflammatory pain, quercetin reduced pain, oxidative stress, and cytokine production.⁸
- Patients with chronic prostatitis who report improvement with quercetin have a reduction in the oxidative stress metabolite F2-isoprostane in their expressed prostatic secretions (EPS). ⁹
- Quercetin therapy reduces inflammation as measured by prostaglandin E2 levels in EPS, and increases the levels of prostatic β -endorphins.¹⁰
- Side effects with quercetin therapy are rare. 11

We propose that the use of Q-Urol will be an effective therapy at reducing symptom burden and distress following prostate brachytherapy procedures due to radiation-induced prostatitis versus a comparator cohort receiving placebo without adding additional toxicity.

2.3 Clinical Experience

In a prospective, randomized, double-blind, placebo-controlled trial of the bioflavinoid quercetin in men with chronic prostatitis, 20% percent of patients taking a placebo and 67% of patients taking the bioflavonoid had an improvement of symptoms of at least 25% as measured by the NIH chronic prostatitis symptom score. In an unblinded open-label follow up study, 82% of patients who received a formulation of quercetin, bromelain, papain and

Version Date: 11APR2023

zinc (Prosta-Q, Farr labs) had at least a 25% improvement in symptom score⁹. The treatment was well tolerated. Out of 30 patients enrolled on the trial, the only adverse events reported were:

- One patient taking placebo developed a rash that resolved when he stopped taking the capsules.
- One patient taking quercetin developed a headache after the first few doses, which resolved
- One patient taking quercetin noted mild tingling of the extremities after each dose. All these side effects resolved after cessation of therapy.

2.4 Effect of Antioxidants on Radiation efficacy

The primary mechanism of antitumor activity from radiation therapy is via the production of chemical radicals perturbing DNA in cancer cells resulting in tumor cell death. Some of the supplements being evaluated in this trial have antioxidant properties, and therefore one could hypothesize that they could produce antitumor activity. In the most exhaustive meta-analysis on the effect of antioxidant use with either chemotherapy or radiotherapy, 49 randomized trials were identified that specifically addressed this concern. The authors determined the following:

"In 17 articles of 49 (approximately 35%) included in this study, effects on patient survival or clinical response during chemotherapy and/or radiotherapy were described. In 7 of 17 RCTs using melatonin supplementation, 4 reported a significantly increased survival rate and 4 reported a significantly increased tumor regression rate. In addition, 1 trial each using vitamin A and multiple vitamins reported a significantly increased survival rate. On the other hand, 2 trials using multiple vitamins reported that there were no significant differences between supplementation and control groups, although the survival rates of the supplementation groups were slightly lower than those of the control groups. Two trials using vitamin E reported that there was no significant difference in clinical response between groups. Also, the RCT using ellagic acid reported that there were no significant differences between groups in survival rate and clinical response. Similarly, a trial using larginine supplementation reported a significant increase in the pathological response. On the other hand, a trial using combination supplement (vitamins C and E and selenium) reported that there was no significant difference in clinical response."

With regard to toxicity, the same authors determined:

"In total, 19 radiotoxicity prevention trials were investigated, which specifically aimed to reduce toxicities affecting the mucosa, skin, salivary glands, and taste. Four of 19 trials reported no significant differences in toxicity between groups. Antioxidant supplements such as vitamin E, multivitamin combination, polyphenol, and zinc were effective in preventing radiation-induced toxicities in the skin, mucosa, and salivary glands."

Patients currently undergoing radiation therapies for prostate cancer at the Huntsman Cancer Institute at the University of Utah are not currently counselled to stop antioxidants or supplements, but asked about supplementation use. There is also no recommendation by the NCCN or any other prostate cancer treatment guideline that suggests antioxidants, phytochemicals, minerals or other supplements should be discontinued. Given the

Version Date: 11APR2023

overwhelming amount of evidence from the randomized controlled trials in the contemporary Yasueda meta-analysis, and the current care standard of allowing antioxidant therapies during prostate cancer radiation therapy, the use of antioxidants and phytochemicals used in this study is considered safe by the best evidence available.

2.5 Rationale of definition of ½ standard deviation of the mean for clinically significant difference on the Patient-Reported Outcomes Measures:

A ½ standard deviation from the mean at the baseline for each PRO-QOL measure or domain was specified as the minimal clinically important difference (MID), to be consistent with established convention and other PCa PRO-QOL outcome studies. ¹³⁻¹⁷ Specifically, a ½ standard deviation was defined as the MID on the landmark ProtecT randomized trial which randomized approximately 1800 men to radiation therapy, versus surgery, versus active surveillance using the same PRO forms (EPIC) used in this study. Utilizing this convention will allow the investigators to compare their outcomes not only against the cohorts in this study, but to historical cohorts such as those in ProtecT, as well as studies funded by the Patient-Centered Outcomes Research Institute (PCORI) evaluating QOL in prostate cancer patients receiving radiation therapy. ^{18, 19}

3 DRUG INFORMATION

3.1 Q-Urol

Q-Urol is an over-the-counter herbal supplement manufactured by Farr Laboratories claiming to have anti-inflammatory effects. It is a combination product composed of quercetin, pollen extract, bromelain, and papain.

3.1.1 Pharmacology

Quercetin is a bioflavonoid found in plants such as onions, berries, green tea, and apples that has antioxidant and anti-inflammatory effects. It is thought to exert its anti-inflammatory effects through mast cell stabilization leading to the inhibition of prostaglandin D₂ formation and the inhibition of the release of histamine, interleukin-8, and TNF.

Rye Flower pollen extract comes from the pollen of rye grass and is often marketed under the name Cernilton. It is been used by men worldwide for the treatment of benign prostatic hyperplasia. Randomized controlled trials have demonstrated some moderate efficacy in the improvement of urological symptoms.^{20, 21} While the mechanism of action is not well understood, it is thought that the efficacy is related to anti-androgenic effects. Rye flower pollen may also act on α-adrenergic receptors to relax the sphincter muscles or by increasing bladder contraction by relaxing urethral smooth muscle tone. Bromelain is a mixture of enzymes found in the fruit and stem of the pineapple plant. Only a small amount of research has been done with bromelain in nasal swelling, inflammation, and the removal of dead skin after burns. Evidence does support its efficacy for relieving acute nasal and sinus inflammation symptoms when used in combination with standard of care medications.²² It is thought to exert its anti-

Version Date: 11APR2023

inflammatory action by reducing leukocyte migration and through inhibition of COX2 expression.^{23, 24} However, those sensitive or allergic to pineapples should not take bromelain.

Papain is a protease isolated from papaya that mediates the hydrolysis of proteins. It is a common ingredient in many products, including toothpaste, contact lens cleaners, meat tenderizers, and meat products However, little research has been done to fully assess its efficacy as an anti-inflammatory. Caution should be taken when used concurrently with warfarin.

3.1.2 Clinical Safety

In a prospective, placebo-controlled, randomized trial, 30 patients with category III chronic prostatitis were randomized to receive quercetin/placebo in a 1:1 ratio. ⁹ Prosta-Q was then administered for 17 additional patients after completion of the randomized portion of the trial. Of the 15 patients randomized to receive quercetin, one experienced a headache after the first few doses and another patient noted mild tingling in the extremities after each dose. Both adverse events resolved on their own upon discontinuation of study therapy.

The group randomized to receive quercetin reported a 35% improvement in the mean NIH symptom score vs. 7.2% reported by the placebo group. However, the 17 patients treated with Prosta-Q reported a mean improvement of 44%.

139 men were treated in a prospective, placebo-controlled, randomized trial of pollen extract in patients with inflammatory chronic prostatitis and chronic pelvic pain syndrome. After 12 weeks of therapy, response (defined as a decrease of the NIH-CPSI total score by at least 25% or at least 6 points) was seen in the pollen extract versus placebo group in 70.6% and 50.0% (p=0.0141). The pollen was well tolerated; two patients reported mild gastrointestinal disorders that caused a short treatment interruption and moderate pain (not otherwise specified) that caused discontinuation of treatment.

4 STUDY DESIGN

4.1 Description

This is a Phase 2, double-blinded, placebo-controlled trial assessing the safety of Q-Urol use after brachytherapy placement in patients with localized prostate cancer. Patients will be randomized in a 1:1 ratio to receive Q-Urol/Placebo twice daily for six weeks after brachytherapy placement. Questionnaires will be administered pre- and post-treatment to assess the change in prostatitis symptoms and quality of life measures. The mean values between groups will be compared.

Once 42 patients (21 to each arm) have been enrolled and treated on the study therapy, enrollment will be placed on hold and an interim analysis conducted. The interim analysis will be conducted for futility and efficacy and will be reviewed by the DSMC. If the analysis is favorable, as defined in the Statistical Analysis section, the trial will open to the enrollment of 98 additional subjects, 49 per arm. However, if the analysis does not demonstrate standards defined in the statistical analysis, the trial will be closed to accrual.

Version Date: 11APR2023

Safety monitoring will be overseen by the DSMC at HCI. See Section 12.4 for safety monitoring plan and early stopping rules.

4.2 Randomization and Blinding

Patients who meet all criteria for enrollment will be randomly assigned to receive Q-Urol (Arm 1) or placebo (Arm 2). Patients will be randomized through the OnCore system in a 1:1 ratio to Arm 1 or Arm 2 and stratified by dose level of brachytherapy used.

To preserve the blind, only the Investigational Drug Services Pharmacy personnel and Data Safety Monitoring Committee (DSMC) at Huntsman Cancer Institute will know treatment assignments. Access to unblinded data/documents will be controlled by the pharmacy to ensure the blind is maintained. Every effort will be made to blind the patient, the investigator, and the study team to the treatment assignment, but the inadvertent unblinding of a patient may occur. If an investigator, site personnel, or patient is inadvertently unblinded, the unblinding will not be sufficient cause for the patient to be discontinued from study treatment or excluded from study analyses. Cases of accidental unblinding will be recorded in the applicable eCRF and evaluated by the DSMC for appropriateness of inclusion in the study analysis.

In the case of an emergency, the treating investigator has the sole responsibility for determining if unblinding of a patient's treatment assignment is warranted. Patient safety must always be the first consideration in making such a determination. If the treating investigator decides that unblinding is warranted, the investigator should contact the investigational pharmacy for treatment assignment.

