6 STRATIFICATION FACTORS

Patients will be stratified by prior use of alpha-blockers for prostate related condition (yes, no) and the dose of brachytherapy: high dose rate (HDR) or low dose rate (LDR).

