11.2 Baseline Characteristics

The following baseline characteristics will be collected from patients at screening (see also Appendix 9):

Version Date: 11APR2023

- Does the patient have a history of Coronary Artery Disease?
- Has the patient had bacterial prostatitis that went away with antibiotics?
- Does the patient have any family history of prostatitis?
- Alcohol history (never used alcohol, current alcohol user, former alcohol user)
- Smoking history (never smoked, current smoker, former smoker)
- Pack years (average number of packs per day and number of years smoked)
- Current employment status (employed, retired, student, unknown, other)
- Insurance status (private insurance, Medicare, Medicaid, VA, military, not insured, self-pay, unknown, other)
- Prostate volume
- Post-void residual urine volume if available
- Prior use of alpha-blockers for symptoms
- The extent of prostate cancer, including location of the cancer relative to the prostate gland capsule

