13.2 Statistical Analyses

13.2.1 Sample size determination

The outcome for sample size determination is the primary endpoint variable, the peak of the National Institutes of Health-Chronic Prostatitis Symptom Index (NIH-CPSI) total score measured from baseline to six weeks post brachytherapy. The primary hypothesis is that the mean of the primary outcome variable will be $\frac{1}{2}$ standard deviation lower in patients taking Q-Urol compared to placebo. A single interim analysis is planned after N1= 21 subjects per group have outcome data. The interim and final analysis will compare the treatment and control means using nominal t statistics (control minus treatment). If the t statistic has a value less than -1.16 at the interim analysis the trial will be terminated for futility. If the t statistic has a value greater than 2.85 at the interim analysis the trial will be terminated for efficacy.

If the study is not terminated for efficacy or futility at the interim analysis an additional N2 = 49 patients per group will be accrued for a total of N = 70 patients per group. If the interim analysis is done at the planned sample size (21 patients per group) the treatment will be deemed efficacious at the final analysis if the t statistic has a nominal value greater than 1.67.

The above design was evaluated using 100,000 simulated data sets for both the null and alternative hypotheses. There is 90% power at overall one-sided Type I error equal to 0.05 (one-sided) to detect a 0.5 standard deviation lower mean of the primary endpoint in the treatment group compared to the control group. The probability of early termination for futility under the null hypothesis is 12%. The probability of early termination for futility under the alternative hypothesis is 0.3%. The probability of early termination for efficacy under the alternative hypothesis is 12%.

If the interim analysis or final analysis is performed at a sample size that is different than the planned sample size the final analysis will be adjusted to maintain an overall Type I error of no more than 0.05 (one-sided).

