13.2.2 Primary endpoint

There are two planned analyses of the primary endpoint variable: an interim analysis at N1 = 21 patients per group and a final analysis at N = 70 patients per group. Two sample *t*- statistics will be calculated and evaluated as described in 13.2.1.

Multiple imputation will be used to replace missing end of treatment values of the National Institutes of Health-Chronic Prostatitis Symptom Index (NIH-CPSI) total score. A sensitivity analysis will replace missing values by the largest (i.e. worst) observed value.

In addition to formal testing for a difference between groups, the mean change between groups and the mean change within each group together will be reported together with 95% confidence intervals.

Version Date: 11APR2023

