13.2.4 Exploratory Analyses

For the analyses involving score changes, the investigators will use ANCOVA in place of 2-sample t-tests, which has been found to be robust to violation of modeling assumptions.

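### Sections 4.2 and 6 list different stratification factors, and the primary t statistics adjust for none of them

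*Combined protocol and SAP*

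**What the plan says.** - **Section 4.2 (Randomization and Blinding)** describes 1:1 assignment through OnCore, "stratified by dose level of brachytherapy used". No other factor is named.
- **Section 6 (Stratification Factors)**: "Patients will be stratified by prior use of alpha-blockers for prostate related condition (yes, no) and the dose of brachytherapy". It then defines the second factor: "the dose of brachytherapy: high dose rate (HDR) or low dose rate (LDR", giving four strata.
- **Section 7.1** describes three brachytherapy prescriptions (LDR alone, LDR with external beam, HDR with external beam). Read without Section 6, the dose level in 4.2 could therefore mean two groups or three.
- **Section 11.2** lists "Prior use of alpha-blockers for symptoms" among the characteristics to collect at screening and points to Appendix 9.
- **Section 13.2.1**: "The interim and final analysis will compare the treatment and control means using nominal t statistics (control minus treatment". Section 13.2.2 adds only that the "statistics will be calculated and evaluated as described in 13.2.1". Neither mentions a stratum term or covariate.
- **Section 13.2.4 (Exploratory Analyses)**: for score changes, "the investigators will use ANCOVA in place of 2-sample t-tests". No covariates are named.

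**The concern.** Someone building the randomisation from 4.2 would produce a different scheme from someone building it from Section 6. The factor at issue matters on the protocol's own terms: Section 6 chose it, Section 2.1 lists alpha-blockers among the mainstay treatments for these symptoms, and the NIH-CPSI total contains urinary items.

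Each reading has its own cost. If alpha-blocker use is not a stratum, its balance is left to chance, most visibly at the interim look with 21 per arm, where the trial can stop. If it is a stratum, an analysis that ignores it uses a standard error that still contains variation the randomisation has removed. The same holds for the brachytherapy stratum, which appears in both lists.

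**Working it through.** **1. Inputs.** From 13.2.1: 21 per arm at the interim and 70 at the end; effect 0.5 SD; one-sided error 0.05; power 90%; cut-offs −1.16 (futility), 2.85 (interim efficacy) and 1.67 (final). From 4.2: 1:1 allocation. The documents do not give the prevalence of prior alpha-blocker use, the factor's R² or the block size. Assumed here: prevalence 40% (range 20–50%), R² 5–20%, permuted blocks of 4. One binary factor stands in for the strata.

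**2. The plan's own figures.** Simulating the two-stage unadjusted test (400,000 data sets per hypothesis, normal outcome, SD 1) gives:

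| Quantity | Stated | Simulated |
|---|---|---|
| Power | 90% | 90.0% |
| One-sided type I error | 0.05 | 0.0503 |
| Futility stop, null | 12% | 12.6% |
| Futility stop, alternative | 0.3% | 0.28% |
| Efficacy stop, alternative | 12% | 12.4% |

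A fixed design would need 69 per arm, and 70 per arm gives 90.5%. The stated design reproduces.

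**3. Only the 4.2 list is built: chance imbalance in alpha-blocker use.** The SD of the between-arm difference in proportions is √(2p(1−p)/n). At p = 0.4:

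- n = 21: √(0.48/21) = 0.151
- n = 70: √(0.48/70) = 0.083

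Across prevalences of 20–50%, a gap above 10 percentage points has probability 42–52% at the interim and 14–24% at the end.

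On the outcome scale, the factor's effect is √(R²/0.24), or 0.46 SD at R² 5% and 0.91 SD at R² 20%. A one-SD imbalance then moves the arm difference by:

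- 21 per arm: 0.151 × 0.46 = 0.07 SD to 0.151 × 0.91 = 0.14 SD
- 70 per arm: 0.083 × 0.46 = 0.04 SD to 0.083 × 0.91 = 0.08 SD

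The target is 0.5 SD.

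**4. Section 6 is built: why the unadjusted test is conservative.** Stratification reduces the true variance of the arm difference by the factor 1−R², but the two-sample standard error does not reflect this. It is too large by 1/√(1−R²), which is 1.03 at R² 5% and 1.12 at R² 20%.

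**5. Two-stage simulation with the factor.** Prevalence 40%, 100,000 data sets per cell, same cut-offs. The Monte Carlo standard error is about 0.07 points for type I error and 0.1 for power.

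| Randomisation | R² | Type I, unadjusted | Type I, adjusted | Power, unadjusted | Power, adjusted | Gain |
|---|---|---|---|---|---|---|
| Stratified on the factor | 5% | 4.5% | 5.0% | 90.6% | 91.3% | 0.7 |
| | 10% | 4.1% | 5.0% | 91.0% | 92.4% | 1.4 |
| | 20% | 3.3% | 5.0% | 92.4% | 94.8% | 2.5 |
| Not stratified on it | 5% | 5.0% | 5.0% | 90.1% | 91.2% | 1.1 |
| | 10% | 5.0% | 5.0% | 90.1% | 92.3% | 2.3 |
| | 20% | 5.0% | 5.0% | 90.1% | 94.7% | 4.6 |

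Gains are in percentage points, from unrounded values. Smaller runs at 40% or 50% prevalence scatter around these figures. With stratification, unadjusted type I error was 4.4–5.0% at R² 5% and 2.9–3.6% at R² 20%, adjusted type I error was 5.1–5.4%, and the gain at R² 5% was about 0.5 points. At R² = 0, adjustment costs nothing with stratification and about 0.2 points of power without it (90.0% versus 89.7%).

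**The case against.** The strongest reply is that the plan already delivers what it promises. Power and error were set for the unadjusted t statistic and both reproduce. Without the alpha-blocker stratum the test keeps about 5% error and 90% power, and its standard error already allows for chance imbalance. With that stratum, unadjusted power is slightly above plan. All of this stands. A reader might infer from the mismatch that balance and precision are simply lost, or that the error rate is broken, but the documents do not support either. Balance is at risk for alpha-blocker use only, and only if the 4.2 list is the one built. The error rate moves in the conservative direction.

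Section 6 is the dedicated section, it defines dose as HDR or LDR, and 4.2 does not say that its factor is the only one. That makes Section 6 the likelier intent, but it does not tell the person configuring OnCore which text governs.

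A reader might also infer from Appendix 9 that alpha-blocker use is not collected. The form as read ends at insurance status and lacks that item, but it also lacks three others from 11.2: prostate volume, post-void residual and cancer extent. These may be on a lost page or taken from the chart, and 11.2 itself requires alpha-blocker use at screening. The point is something to confirm, not a demonstrated gap.

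A large R² is also open to doubt. The two urinary items supply at most 10 of the 43 NIH-CPSI points (Appendix 1), and Section 5.2.1 excludes baseline AUA scores above 15. Finally, ANCOVA does appear in 13.2.4, but it is exploratory, concerns score changes and names no covariates, so it does not settle the primary comparison.

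**Conclusion.** The point holds in a limited form. The two stratification lists differ in the current text, and the primary comparison adjusts for neither factor. The planned 90% power and 0.05 one-sided error remain correct for the unadjusted test.

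What is given up is efficiency. Under Section 6, the test runs at roughly 4.5% down to 3% instead of 5% and forgoes about 0.5 to 2.5 points of power. Under the 4.2 list, alpha-blocker balance is left to chance and adjustment would gain about 1 to 4.6 points. The mismatch and the absence of a stratum term can be read directly from the text. The sizes rest on assumed R² (5–20%), prevalence and block size. If the factors are weakly prognostic, the loss is negligible.

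**What to change.** 1. Make 4.2 match Section 6: prior alpha-blocker use (yes/no) and HDR versus LDR. If OnCore already follows one scheme, record which.
2. Confirm that alpha-blocker use is captured at screening, as 11.2 requires, under one definition (11.2 and Section 6 word it differently). If Appendix 9 does lack the item, add it.
3. In 13.2.1 and 13.2.2, prespecify a linear model with treatment and both stratification factors for the interim and final primary comparisons, before any unblinded look. If the unadjusted test is kept, give the reason.
4. Confirm the −1.16, 2.85 and 1.67 cut-offs by simulation under that model with the actual strata and block size. The simulations here put adjusted type I error at about 5.0% in the large run and 5.1–5.4% in smaller ones, so little change is expected, but the cut-offs were derived for a two-sample t statistic.

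The cost is protocol wording, possibly one form item, slightly more analysis work and a repeat of the design simulation. No patients are added.
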